5.3.3 Sensitivity analysis

A sensitivity analysis will evaluate the treatment difference between individual oral NNC0385-0434 doses and placebo using the same analysis as the primary analysis for the primary estimand described above, but with baseline LDL-C not included as a covariate in the model.

5.4 Secondary endpoints analyses

5.4.1 Confirmatory secondary endpoints

Not applicable for this trial.

5.4.2 Supportive secondary endpoints

The following supportive secondary endpoints

- change in total cholesterol
- change in HDL-cholesterol
- change in VLDL-cholesterol
- change in triglycerides
- change in total Apo B
- change in total Apo CIII

are computed similar as the primary endpoint, that is for each of these six lipid/lipoprotein parameters, the percentual change from randomisation at week 0 to week 12 is defined as:

$$\% \text{ parameter change} = \frac{(\text{parameter value at week 12} - \text{parameter value at baseline})}{\text{parameter value at baseline}} \times 100\%$$

Each of these six endpoints will be analysed separately by an analysis of covariance (ANCOVA) with randomised treatment (each oral NNC0385-0434 dose, pooled placebo group, and s.c. evolocumab) and strata as factors (population strata (inclusion criteria 3a/3b), country (Japan/non-Japan)) and baseline parameter value as a covariate.

The parameter Lipoprotein a (Lp(a)) follows a log-normal distribution and will be log-transformed before analysis. The supportive secondary endpoint: Change in total Lp(a) (from baseline (week 0) to visit 9 (week 12)), will be reported as the result of the difference in log-transformed Lp(a) back-transformed to the original scale, implying that log-treatment-differences are reported as treatment ratios. Confidence intervals for the treatment ratios will be calculated as exponential upper and lower limits for log-treatment difference confidence intervals.

Safety endpoints

The secondary endpoint Treatment-emergent adverse events (TEAE) is the number of AEs recorded during the on-treatment period (see [section 4](#) for the definition of the on-treatment period). All AEs will be coded using the most recent version of the Medical Dictionary for Regulatory Activities (MedDRA)

Summaries of TEAEs are presented as an overview including all AEs, serious AEs, AEs leading to withdrawal, AEs by severity, AEs by relation to treatment and outcome of AEs. Furthermore, summary tables based on system organ class and preferred term is made for:

- All TEAEs
- Serious TEAEs
- TEAEs evaluated to be probably or possibly related to the trial products
- TEAEs by severity
- Serious TEAEs evaluated to be probably or possibly related to the trial products

5.5 Exploratory endpoints analysis

5.5.1 PK sub-study exploratory endpoints

Below the exploratory endpoints related to the PK sub-study are defined and the planned analyses are presented.

The following PK endpoints will be derived at steady state from 0 to 24 hours after the last dose of oral NNC0385-0434 on visit 9 (week 12):

- $AUC_{0-24h,0434,SS}$: area under the steady state plasma NNC0385-0434 concentration–time curve
- $C_{max,0434,SS}$: maximum observed plasma NNC0385-0434 concentration at steady state
- $t_{max,0434,SS}$: time to maximum observed plasma NNC0385-0434 concentration at steady state, in case this is not uniquely determined, the lowest value will be chosen.

The following exploratory endpoint will be derived at steady state after the last dose of oral NNC0385-0434 on visit 9 (week 12):

- $t_{1/2,0434,SS}$ terminal phase elimination half-life of NNC0385-0434 at steady state

The following exploratory endpoint will be derived from 0 hours to infinity at steady state after the last dose of oral NNC0385-0434 on visit 9 (week 12):

- $AUC_{0-\infty,0434,SS}$: area under the steady state plasma NNC0385-0434 concentration–time curve

Subjects included in the PK sub-study that discontinue treatment, but will complete visit 9X, will have derived PK endpoints after the last dose of oral NNC0385-0434 on Visit 9X.

The oral NNC0385-0434 PK endpoints will be derived as stated in the table in [appendix 6.3](#).

Each of the PK endpoints will be summarised descriptively by dose level of oral NNC0385-0434 (15, 40 and 100 mg) and country (Japan/non-Japan).

The endpoint $AUC_{0-24h,0434,SS}$ will be analysed by a linear mixed model based on the log-transformed values. The model will include country (Japan/non-Japan) and dose level of oral NNC0385-0434 (15, 40 and 100 mg) as fixed factors, and the difference between the 2 levels in the country factor will be interpreted as a race difference. The estimated race difference will be transformed back to the original scale and presented as the race ratio with two-sided 95% confidence interval.

A sensitivity analysis using the above model including body weight at baseline as a covariate will also be done.

The same analyses as described above for $AUC_{0-24h,0434,SS}$ will be performed for $C_{max,0434,SS}$.

5.5.2 NNC0385-0434 concentration and NNC0385-0434 binding antibodies endpoints

Each of the endpoints related to the NNC0385-0434 concentration and the NNC0385-0434 binding antibodies:

- Concentration of NNC0385-0434 at steady state
- Occurrence of NNC0385-0434 binding antibodies
- Occurrence of NNC0385-0434 binding antibodies cross reacting with endogenous counterpart (EGF-A)
- Titre of NNC0385-0434 binding antibodies

will be presented in a listing.

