Biosamples for Genetic (future analysis)	8.10 10.6				X														
Administration of Trial Product					X			X			X	X	X	X ^e	X				
IWRS Session					X	X		X			X	X	X	X	X				
Drug Dispensing						X		X			X	X	X	X ^e	X				
Hand Out ID Card					X														
Hand Out Direction for Use						X		X											
End of Trial																			X

Notes:^a Date of birth, age, sex, race and ethnicity (according to local regulation). Germany, The Netherlands: For country-specific requirements, please refer to Appendix 9 (Section [10.9](#)).^b Patients will receive a meal 30-60 min post dosing, and the PK sampling should be performed 60-90 minutes post dosing.

Date and exact time point for trial product ingestion at site, including start of meal must be collected in the laboratory requisition form.

Protocol
Trial ID: NN6435-4697

Date: 28 September 2021 | Status: Final | **Novo Nordisk**
Version: 3.0 | Page: 13 of 96

^c Fasting for blood sampling is defined as no food or liquid within the last 8 hours prior to blood sampling, however water is allowed up until 2 hours prior to blood sampling.

^d Pre-dosing

^e Only applicable for patients in the PK sub-study to cover one dose given at site. Sampling scheme for PK sub-study is outlined in [Table 1-2](#).

^f V9X is only applicable for patients in the PK sub-study who have discontinued trial product prematurely. Visit 9X has to be performed as soon as site has been informed of prematurely trial product discontinuation by the patient.

^g Patients part of the PK sub-study who discontinue treatment will be requested to take their last trial product dose at site and attend visit 9X followed by visit 9A, 9B, 9C and 9D.

^h Visit 9 + 1 day (24 hours)

Abbreviations: ECG: Electrocardiogram; IWRS: Interactive web response system; P: Phone visit; PCSK9: proprotein convertase subtilisin/kexin type 9; PK: pharmacokinetics; V: Clinic visit

Table 1-2 Sampling scheme for PK sub-study^a

Visit	Week no.	Nominal time ^c	Time window allowance	Dosing of IMP	NNC0385-0434 PK
V9	Week 12	-15 min	-		X ^e
		0 hour	-	X ^d	
		1 hour	0 to 30 min		X
		2 hours	±15 min		X
		4 hours	±1 hour		X
		8 hours	±2 hours		X
V9X ^b		-15 min	-		X ^e
		0 hour	-	X ^d	
		1 hour	0 to 30 min		X
		2 hours	±15 min		X
		4 hours	±1 hour		X
		8 hours	±2 hours		X
V9A	V9/V9X + 1 Day	24 hours	±4 hours		X
V9B	V9/V9X + 1 Week	7 days	±3 days		X
V9C	V9/V9X + 2 Weeks	14 days	±3 days		X
V9D	V9/V9X + 3 Weeks	21 days	±3 days		X

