4.1.1 PK sub-study

A PK sub-study in Japanese and non-Japanese patients will be performed following the 12 weeks of treatment. For PK sampling details, refer to [Table 1-2](#).

For the PK sub-study, 30 Japanese and 30 non-Japanese patients will be randomised with ratio 3:1:3:1:3:1:3 as randomised in the main trial (for details on randomisation ratio, refer to [Figure 4-1](#)). For further details on randomisation, see Section [6.3.1](#).

The aim of the PK sub-study is to assess and compare the PK properties of three doses of oral NNC0385-0434 at steady-state between Japanese and non-Japanese patients (18 Japanese and 18 non-Japanese patients exposed to NNC0385-0434). The evolocumab arm is not part of the PK sub-study. Therefore, patients randomised to the evolocumab arm will not have additional visits or sub-study PK samples taken.

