4.2 Scientific rationale for trial design

To allow evaluation of dose-response relationship of oral NNC0385-0434, a parallel randomised, double-blinded within dose level, controlled design has been chosen. To minimize bias in the assessment, the oral NNC0385-0434 treatment arms are double-blinded for each dose level of oral NNC0385-0434 with size-matched placebo arm. Three dose levels of NNC0385-0434, covering the expected range for clinically adequate LDL-C lowering, have been chosen to evaluate the dose-response relationship.

The rationale for including a s.c. evolocumab arm is to compare the efficacy of oral NNC0385-0434 against one of the already marketed PCSK9 inhibitors. The s.c. evolocumab arm is open-label to limit unnecessary injections (e.g., by use of double-dummy) as the primary aim of the trial is to investigate the effects of oral NNC0385-0434.

The trial population will consist of patients with established ASCVD or ASCVD risk on maximally tolerated statin dose and other lipid-lowering therapy requiring further LDL-C lowering. In alignment with the European ESC/EAS treatment guideline^{4,5}, this is the target population that will benefit of obtaining LDL-C < 1.8 mmol/L (<70 mg/dL) in order to reduce their ASCVD risk. Specific LDL-C inclusion criteria have been defined for Japanese patients according to the Japanese guidelines for prevention of ASCVD (JAS guidelines)⁶.

The treatment period is set to 12 weeks. The steady state exposure is expected to be reached at approximately 6 weeks into the trial and therefore the complete LDL-C lowering response should be observed within 12 weeks of treatment.

As a precautionary measure, 15 patients will be recruited initially before recruitment of the remaining 240 patients. Medical monitoring of minimum 4 week safety data for these 15 patients will be completed before dosing of the remaining 240 patients in the trial (see Section [10.1.8.2](#)).

PK sub-study

The rationale for including the PK sub-study is to assess and compare the steady state PK profiles of multiple doses of oral NNC0385-0434 in Japanese and non-Japanese patients. Therefore, PK assessments from the evolocumab arm are not relevant and this arm is not included in the PK sub-study.

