8.11 Immunogenicity assessments

Anti-drug antibody samples will be collected according to the flowchart ([Table 1-1](#)). All samples must be drawn prior to trial product administration if trial product administration is planned on the sampling day.

Assessment of antibodies against NNC0385-0434 (anti-drug antibodies) in serum will be performed at Novo Nordisk A/S.

For details on blood sampling, serum preparation and storage, please refer to the laboratory manual.

Analysis for anti-drug antibodies in patients treated with NNC0385-0434 will be done as listed in the flowchart ([Table 1-1](#)) with a binding anti-drug antibody assay. Positive samples will be further characterised for neutralising activity by correlation to PK and PD (with a validated LDL-C assay) i.e. the highly sensitive PD marker LDL-C. Any potential clinical effect of ADAs will be evaluated by correlation to PK, efficacy and safety parameters. Detailed description of the anti-drug antibody assay methods will be included in an analytical report. Antibody assays will be validated according to international guidelines and recommendations. Furthermore, samples will be banked for possible future analysis in a dedicated neutralising anti-drug antibody analysis if this assay would be deemed necessary (for further details, see Section [10.6.2](#)).

Results from the binding anti-drug antibody analyses from visit 2, 4, 6, 8, 9 and 10 will be available at the end of trial.

At the end of the trial, the following data will be electronically transferred to the Novo Nordisk database:

- Anti-NNC0385-0434 binding antibodies (positive/negative)
- Anti-NNC0385-0434 binding antibodies cross-reacting with endogenous EGF-A (positive/negative)
- Anti-NNC0385-0434 binding antibody titre (no unit)

Patients who have tested positive for antibodies against NNC0385-0434 (high titre of antibodies) at visit 10 (end-of-trial visit) will be requested to have a follow-up analysis performed 12 months after visit 10. If the anti-NNC0385-0434 antibody titre has not declined at the follow-up analysis, the patient may be requested to have an additional follow-up analysis performed. The result from additional follow-up analyses will be reported in a separate analytical report. Thus, the results will not be part of the CTR.

The investigator will not be able to review the results of antibody measurements in relation to AEs as these will be analysed after LPLV.

Refer to Section [10.6.2](#) for further details.

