- Timepoint 3: After PK data is available from visit 8 (9 weeks after dosing) for the initial 15 patients and from visit 4 (2 weeks of dosing) for the following 20 patients.

Further details are described in the interim modelling analysis plan.

The Novo Nordisk NN6435 Safety Committee will be informed immediately in case any of the following criteria are met:

- if the exposure of NNC0385-0434 exceeds the NOAEL exposure observed in the 13-week non-clinical toxicity study (12 mg/kg/day s.c. + 50 mg/kg/day orally)
- if the geometric mean C_{max} of NNC0385-0434 for patients treated with any dose arm of NNC0385-0434 is numerically higher than the geometric mean C_{max} observed in the FHD trial NN64334-4493 (11,015.5 nmol/L).

The initial 15 patients (3 patients in each active treatment arm and 1 patient in each of the placebo arms) will be recruited and treated for minimum 4 weeks before recruitment of the remaining 240 patients. Recruitment of the remaining patients will be initiated following medical monitoring of 4 week data of these 15 patients without identification of safety concerns, in addition to review of PK data from the 15 patients 2 weeks after dosing

If unexpected safety findings occur, a Novo Nordisk Safety Committee will be informed immediately and will take appropriate actions to the information received.

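### Does the SAP need to specify the antibody evaluation that protocol 8.11 promises, when SAP 5.5.2 only lists the results?

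*SAP*

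**What the plan says.** Protocol 8.11 makes two commitments. On neutralisation: "Positive samples will be further characterised for neutralising activity by correlation to PK and PD", with LDL-C as the PD marker. On consequences: "Any potential clinical effect of ADAs will be evaluated by correlation to PK, efficacy and safety parameters". A dedicated neutralising assay is held in reserve. On timing, "Results from the binding anti-drug antibody analyses from visit 2, 4, 6, 8, 9 and 10 will be available at the end of trial".

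Protocol 9.4.4 and 9.4.6 send exploratory and other analyses to the SAP. SAP 5.5.2 names four endpoints (steady-state concentration, binding antibodies, EGF-A cross-reactivity, titre) and says that each "will be presented in a listing". SAP Appendix 6.3 gives no derivation for them, and SAP 5.7 and 5.7.2 are marked not applicable. SAP 5.7.1 refers population PK and exposure-response work to a modelling analysis plan due before database lock. Antibodies are not among its example covariates, but the list is illustrative. SAP Appendix 6.2 declares no departure from the protocol.

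**The concern.** The protocol promises an evaluation and hands the detail to the SAP, and the SAP returns a listing. A listing shows values but does not say which comparison will be made. It also leaves open which antibody result is paired with which LDL-C and concentration value.

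The stake would be dose selection. The Emax model is fitted to arm means (SAP 5.3.2). If antibodies neutralised the drug mainly at the top dose, the 100 mg mean would be pulled up towards the 40 mg mean, and the curve would flatten much as it would under true saturation. The two explanations carry different messages for phase 3. LDL-C by antibody status within dose is a natural first look at the question, and no SAP section specifies it.

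The flowchart seemed to sharpen the pairing problem. Its visit 9 pre-dose PK mark carries a footnote reading "Only applicable for patients in the PK sub-study to cover one dose given at site". The sub-study has "18 Japanese and 18 non-Japanese patients exposed to NNC0385-0434", which is 36 of the 3 × 51 = 153 patients on active oral drug (24%). On that reading visit 8 would be the only visit after week 6 with an antibody result and a concentration for everyone.

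**Working it through.** **1. Is the evaluation placed anywhere?** The possible homes, side by side:

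| Place | Covers | Names the 8.11 evaluation? |
|---|---|---|
| SAP 5.5.2 and 6.3 | Listing of individual values | No |
| SAP 5.6 with protocol Table 10-2 | Antibodies are classed as safety laboratory tests; these are reported descriptively | No link to LDL-C or PK |
| SAP 5.7.1 | Population PK, exposure-response, separate plan | Not named; covariate list open |
| Protocol 8.11 analytical report | Assay methods | No |
| Protocol 8.11.1 | Work-up after a systemic hypersensitivity reaction | Separate purpose |

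So the evaluation is promised and not withdrawn, but not assigned to a document. The modelling analysis plan was not available, so the accurate statement is that its place is not stated. That is different from saying it is not planned.

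**2. Does the visit 9 reading hold?**

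- The footnote sits on the pre-dosing sub-row, and also on the trial product administration and dispensing rows. Its wording concerns a dose given at site. That fits a narrower meaning: only sub-study patients are dosed at visit 9, so only they have a sample that is pre-dose.
- The parent PK sampling row carries no such footnote. It has 12 marks in both Table 1-1 and Table 10-4, matching V2, V4, V6, V7, V8, V9, V9X, V9A, V9B, V9C, V9D and V10.
- The concentration endpoint is listed outside the PK sub-study block and runs from visit 7 to visit 9. Protocol 4.2 agrees with that start: "The steady state exposure is expected to be reached at approximately 6 weeks into the trial".
- The table text is damaged: the pre-dosing row shows 7 marks in Table 1-1 and 5 in Table 10-4. A count of 117 missing samples (153 − 36) cannot rest on one superscript there.

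Intersecting the stated schedules: antibody visits {2, 4, 6, 8, 9, 10} and concentration visits {7, 8, 9} share {8, 9}. Adding the LDL-C endpoint visit leaves {9}. Visit 8 sampling is not in doubt (protocol 10.1.8.2 plans a review "After PK data is available from visit 8 (9 weeks after dosing) for the initial 15 patients"), but nothing shows that it is the only usable visit.

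**3. How large could the effect be?** Inputs: planned LDL-C changes of −28, −46 and −60% at 15, 40 and 100 mg (protocol 4.3); SD 30 points and 51 per arm (protocol 9.2). Assumed: placebo change 0; a fraction f of patients loses the whole drug effect.

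Least-squares fit of E0 + Emax·d/(ED50 + d) to the planned means: Emax −75.2, ED50 25.3 mg.

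| f | 100 mg mean, loss at 100 mg only | ED50, loss at 100 mg only | ED50, equal f at all doses | Emax, equal f |
|---|---|---|---|---|
| 10% | −54.0 | 18.5 | 25.3 | −67.6 |
| 20% | −48.0 | 13.3 | 25.3 | −60.1 |
| 30% | −42.0 | 9.2 | 25.3 | −52.6 |

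With 12 of 51 affected at 100 mg only, the mean is −60 × (1 − 12/51) = −45.9 and ED50 is 11.7 mg. The 40-to-100 mg gap of 14 points closes when f = 14/60 = 23%. If affected patients lose half the effect, it closes when f = 14/30 = 47%.

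**4. What would a by-status comparison show?** Half-width of the 95% CI within a dose = t(0.975, 49) × 30 × √(1/n₊ + 1/n₋). This gives 35.9 for 3 vs 48, 28.4 for 5 vs 46, and 19.9 for 12 vs 39. A 60-point loss at 100 mg would be visible. A 28-point loss at 15 mg would be marginal at 5 positives (about 10%).

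**The case for a change.** The strongest case for a change is that the correlation to PK and LDL-C is the only neutralisation assessment the protocol commits to, since the dedicated assay is contingent. Antibodies are analysed after the last patient's last visit, and protocol 6.3.3 gives the antibody laboratory and the responsible immunogenicity scientist access to treatment allocation. Without a written rule, the definition of positivity, the visit and the comparison could be settled with results in hand. A few descriptive tables would need no new samples.

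Part of this stands. No SAP section points to the evaluation, and a listing does not define one. The documents also do not show whether 8.11 read the same when the SAP was approved: the SAP cites protocol version 2.0, and the protocol supplied is version 3.0.

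It does not carry further, for three reasons. First, 8.11 speaks of correlation and promises neither a test nor a table; no error rate or confirmatory claim hangs on the choice. Second, a by-status comparison would not settle neutralisation against saturation. Antibody status arises after randomisation, binding is not neutralisation, and status may track exposure, so a difference in LDL-C could be confounded. Third, fixing visit 8 as the pairing visit, with visit 9 concentrations confined to the sub-study, could lose most concentrations at the one visit where antibody, LDL-C and PK endpoints coincide.

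**Conclusion.** No change to the plan is called for. The SAP leaves an exploratory evaluation undescribed, and analysts can fill that sensibly: the commitment is in the protocol, the antibody, LDL-C and concentration data are collected, the individual antibody and concentration values are listed, and same-visit pairing at visits 8 and 9 follows from the stated schedules.

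The primary comparison, its hierarchical testing, the sample size and the arm means used in the dose-response fit are unaffected at any antibody rate; only the interpretation of a flat top could be. A shift in ED50 from 25.3 to 11.7 mg needs complete loss of effect in 12 of 51 patients at the highest dose and none elsewhere. That rate is close to the 14/60 that closes the 40-to-100 mg gap, and it is not an estimate from the documents. Under equal loss at every dose ED50 stays at 25.3 mg and only Emax shrinks.

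Two things remain unknown: what the modelling analysis plan contains, and the exact visit 9 PK marking in the flowchart. Neither would change the conclusion, because the objective is exploratory under either answer.

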5.6 Other safety analyses

All safety analyses will be made on the safety analysis set. The standard safety assessments (AEs, safety laboratory parameters, vital signs, etc.) will be reported descriptively; including any notable changes of clinical interest in laboratory parameters.

5.7 Other analyses

Not applicable for this trial.

5.7.1 Other derivations and assessments

Population PK and exposure-response analyses will be used as supportive evidence for the evaluation of efficacy and safety as well as to support the dose selection of oral NNC0385-0434 for future clinical development in patients with established ASCVD or ASCVD risk. Firstly, plasma NNC0385-0434 concentrations will be analysed using a population PK model, quantifying covariate (such as baseline body weight, age, sex, race, ethnicity) effects on oral NNC0385-0434 exposure. Secondly, model-based estimates of steady-state average concentrations will be derived for each patient, to facilitate subsequent exposure-response analyses. Relevant efficacy and safety endpoints will be related to steady-state average concentrations and subjected to model-based analysis.

A modelling analysis plan will be prepared before data base lock, outlining details of the analyses. The modelling will be performed by Quantitative Clinical Pharmacology at Novo Nordisk and will be reported separately from the CTR.

